9.1.9 Hypersensitivity and adverse reactions

The grading for infusion-related reactions according to the NCI Common Terminology Criteria for Adverse Events (CTCAE) version 5.0 (Jun 2017) is provided in [Table 9-4](#). In the event of a severe or life-threatening (ie, Grade 3 or 4) infusion reaction, the study participant must permanently discontinue IMP and be managed as described in Section [18.1](#).

Table 9-4: Infusion-related reaction grading according to the NCI Common Terminology Criteria for adverse events version 5.0 (Jun 2017)

Grading	Infusion-related reaction
1	Mild transient reaction: infusion interruption not indicated; intervention not indicated
2	Moderate: Therapy or infusion interruption indicated but responds promptly to symptomatic treatment (for example, antihistamines, NSAIDs, narcotics, iv fluids); prophylactic medications indicated for $\leq 24\text{h}$
3	Severe: Prolonged (eg, not rapidly responsive to symptomatic medication and/or brief interruption of infusion); recurrence of symptoms following initial improvement; hospitalization indicated for clinical sequelae
4	Life-threatening consequences; urgent intervention indicated
5	Death

iv=intravenous; NCI=National Cancer Institute; NSAID=nonsteroidal anti-inflammatory drugs

In case of occurrence of a hypersensitivity reaction (except for local injection site reaction) and depending upon its severity, appropriate countermeasures will immediately be taken by the investigator. In the event the infusion reaction occurs during a home visit, the home nurse will be trained to follow all steps as detailed in the study manual and will liaise with the investigator for the proper handling of the case. Serum complement (C3, C4), plasma complement (C3a, C5a), and serum cytokine samples must be collected from study participants experiencing infusion reactions ([Table 5-2](#)).

If the investigator does not initially choose to discontinue the infusion of IMP and symptoms persist or escalate during continued infusion, the infusion should be stopped. In case of any severe infusion reaction(s), the infusion of IMP must be stopped immediately and appropriate treatment initiated, as necessary, at the discretion of the investigator and in accordance with the SOC. When infusion reactions occurred while the IMP has not been stopped, the investigator should closely assess the adequacy of home administrations (refer to [Section 8.2](#)) and consult with UCB Study Physician before considering home administration after the infusion reactions.

Suspected anaphylactic reactions should be diagnosed using Sampson's Criteria (Sampson et al, 2006) as described in [Section 18.2](#). In the event of an anaphylactic reaction meeting Sampson criterion 1 or 2, the infusion must be discontinued immediately and emergency resuscitation measures implemented.

9.1.10 Management of headache

Based on current available clinical data, headache is the most commonly reported adverse drug reaction in study participants treated with rozanolixizumab. Study participants should be well informed of this potential adverse drug reaction and should be instructed on how to manage it.

Treatment of headaches should be as per national guidelines and take medical history of previous headaches, concomitant medication, and co-morbidities (eg, asthma) in consideration. In case of continued tolerance issues, and if symptomatic headache medication (eg, acetylsalicylic acid

1000mg) is not sufficient, a further step can be to reduce dose of IMP to █ (see Section 7.2).

Determination of the severity of headache will be consistent with National Cancer Institute CTCAE version 5.0. Severe headache is defined as severe pain limiting self-care activities of daily living (ADL). Self-care ADL refer to bathing, dressing and undressing, feeding self, using the toilet, taking medications. Treatment of headache will be provided as clinically indicated according to the national guidelines.

Study participants experiencing severe and/or serious headache will complete the Headache Questionnaire daily until resolution (ie, if headache becomes nonserious, moderate or mild, or completely resolved, whichever comes first). At the clinic visit when the severe headache is reported, the Headache Questionnaire will be followed by a neurological assessment (including fundoscopy). If the severe or serious headache is initially reported at a home visit or during a telephone call, the study participant should be reviewed at the study site as soon as is practically possible for further investigations. Study participants should be monitored for signs and symptoms suggestive of central nervous system involvement and evaluated immediately if other causes (eg, meningitis, intracranial bleeding) are suspected. Further neurological workup may be performed (if indicated) at the discretion of the investigator and may include a computed tomography scan, magnetic resonance imaging and/or a lumbar puncture for cerebral spinal fluid collection. In addition, samples for exploratory safety biomarkers should be collected for study participants experiencing severe or serious headache when possible (Table 5-2). These investigations will be performed to further understand the mechanism of headache in these study participants.

Details of neurological examination to be performed are provided in Section 9.3.4. The Headache Questionnaire will be provided in the study procedures manual.

9.1.11 Management of moderate or severe diarrhea

Moderate or severe diarrhea is defined as an increase of ≥ 4 stools per day over Baseline or incontinence due to urgency of diarrhea or new/prolonged hospitalization for management of diarrhea or limiting self-care ADL or life-threatening consequences requiring urgent medical intervention. Determination of the severity of diarrhea will be consistent with CTCAE version 5.0.

Stool collection and analysis will be performed for study participants reporting moderate or severe diarrhea. The frequency of stool sampling will be as clinically indicated in the opinion of the investigator and assessed per local guidance. Analysis of stool samples will be performed locally. In addition, collection of blood samples for the assessment of exploratory safety biomarkers is required for study participants with severe GI disturbances including diarrhea.

Treatment of diarrhea will be provided as clinically indicated according to the local guidelines.

9.2 Laboratory measurements

Blood and urine specimens for routine assay of hematology, clinical chemistry, and urinalysis testing, as well as pregnancy testing and serology testing will be performed according to the schedule of assessments (Table 5-1) to monitor the safety of study participants. All parameters will be assessed by the designated central laboratory with the exception of the urine pregnancy

test prior to each dose. Specific details regarding the handling and processing of serum chemistry, hematology, and urinalysis samples are provided in the study laboratory manual.

The following laboratory parameters will be measured as detailed in [Table 9-5](#).

PUBLIC COPY
This document cannot be used to support any marketing application and any extensions or variations thereof.

Table 9-5: Laboratory measurements

Hematology	Chemistry	Urinalysis ^a
Hemoglobin	ALP	pH
Hematocrit	ALT	Protein
RBC	AST	Glucose
WBC (including differential)	GGT	Ketone
Platelet count	Total bilirubin ^b	Urobilinogen
	LDH	Bilirubin
	Creatine kinase	Blood
Serology ^c	Total protein	Nitrite
HBsAg, HBcAb	Albumin	Leukocytes
HCV Ab	Alpha- and beta-globulins	
HIV (anti-HIV1 or anti-HIV2 antibodies)	Urea-nitrogen	
Tuberculosis	Creatinine	Albumin
	Triglycerides	Creatinine
	Total-cholesterol	
	LDL cholesterol	Pregnancy test
	HDL cholesterol	Serum HCG ^d
	Electrolytes (calcium, phosphate, sodium, potassium, chloride, and magnesium)	Urine HCG ^e
	Amylase	
	hsCRP	
	Procalcitonin	
	HbA1c ^f	

Ab=antibody; ALP=alkaline phosphatase; ALT=alanine aminotransferase; AST=aspartate aminotransferase; GGT=gamma-glutamyltransferase; HBcAb=hepatitis B core antibody; HBsAg=hepatitis B surface antigen; HCG=human chorionic gonadotropin; HCV=hepatitis C virus; HDL=high density lipoprotein; HIV=human immunodeficiency virus; hsCRP=high sensitivity C-reactive protein; IGRA=interferon gamma release assay; IMP=investigational medicinal product; LDH=lactate dehydrogenase; LDL=low density lipoprotein; RBC=red blood cell; WBC=white blood cell

^a Urine microscopy will be performed if urine is positive for protein, blood, nitrite, or leukocytes.

^b Direct bilirubin will also be measured when total bilirubin is elevated.

^c Serology performed at Screening only. An IGRA should be performed for active or latent tuberculosis testing.

^d Serum pregnancy test performed) only for women of childbearing potential when study participant enters CIDP04 (either at Screening [Visit 1] or Baseline [Visit 2]).

^e Urine pregnancy test (dipstick) for women of childbearing potential performed prior to dosing (and confirmed negative) at dosing visits and each visit of the Observation Period. Note that the final urinary pregnancy test of the study should be no longer than 90 days after the final dose of IMP.

^f Performed at Screening only.

9.2.1 Evaluation of PDILI

The PDILI IMP discontinuation criteria for this study are provided in Section 6.4.2, with the accompanying required follow-up investigation and monitoring detailed below. All PDILI events must be reported as AEs and reported to the study site and sponsor within 24h of learning of their occurrence. Any PDILI event that meets the criterion for potential Hy's Law must be reported as an AE of special interest, and, if applicable, also reported as an SAE (see Section 9.1.1.2).

Evaluation of PDILI consists of the diagnostic testing and continued monitoring included in Table 9-6 (specific tests dependent on laboratory results and corresponding symptoms) and consultation with a local hepatologist (if applicable; discussed in Section 9.2.1.1). The local hepatologist is the expert usually consulted by the treating physician for assessment and management of potential hepatic disease. This would usually be a hepatologist, but may be a gastroenterologist. Additional investigation and monitoring may be required and adapted based on the diagnosis after the cause of the liver injury/abnormality is confirmed (details in Section 9.2.1.4).

The results of all monitoring, including laboratory testing and other testing, should be made available to the study site and sponsor.

All initial tests resulting in abnormal hepatic laboratory values need to be repeated, but appropriate medical action must not be delayed waiting for the repeat result.

If tests are done locally for more rapid results, a concurrent sample should also be sent to the central laboratory whenever possible. Medical care decisions are to be made initially using the most rapidly available results and a conservative approach must be taken if the results from the 2 laboratory tests are significantly different. Data from the local and central laboratory are to be recorded on the applicable eCRF pages.

When IMP is discontinued, all concomitant medications and herbal supplements that are not medically necessary should also be discontinued. In these cases, the investigator should also consider dose reduction for medically necessary concomitant medication and consider changing any medically required concomitant medication known to be hepatotoxic to a suitable alternative.

When IMP is stopped due to PDILI (as described in Section 6.4.2), IMP must be permanently discontinued unless a subsequent alternative diagnosis fully explains the hepatic findings. If a subsequent alternative diagnosis fully explains the hepatic findings, and the requirements provided in Section 9.2.1.2.1 are met, rechallenge with IMP may be appropriate.

Rechallenge with a substance potentially causing drug-induced liver injury is dangerous, may be fatal, and must not occur.

Table 9-6 summarizes the approach to investigate PDILI.

Table 9-6: Required investigations and follow up for PDILI

Laboratory value		Symptoms ^a of hepatitis or hypersensitivity	Immediate		Follow up	
ALT or AST	Total bilirubin		Consultation requirements	Actions	Testing	Evaluation
≥3xULN	≥2xULN ^b	NA	Hepatology consult. ^c Medical Monitor must be notified within 24 hours (eg, by laboratory alert) and study participant discussed with Medical Monitor ASAP.	Immediate, permanent IMP discontinuation.	Essential: Must have repeat liver chemistry values and additional testing completed ASAP (see Section 9.2.1.3); recommended to occur at the site with HCP.	Monitoring of liver chemistry values at least twice per week until values normalize, stabilize, or return to within Baseline values. ^d
≥3xULN	NA	Yes		Immediate, temporary or permanent, IMP discontinuation.		
≥3xULN (and ≥2x Baseline) and <5xULN	<2xULN	No	Discussion with Medical Monitor required if the criterion that allows for IMP continuation is met.	Further investigation – immediate IMP discontinuation not required (see Section 9.2.1.2).	Not required unless otherwise medically indicated (at discretion of investigator).	
≥5xULN (and ≥2x Baseline)	<2xULN	No	Discussion with Medical Monitor required. Hepatology consult required if ALT or AST ≥8xULN	Immediate, permanent IMP discontinuation.	Essential: Every attempt must be made to have repeat liver chemistry values and additional testing completed within 48 hours at the site with HCP (see Section 9.2.1.3).	Monitoring of liver chemistry values at least twice per week until values normalize, stabilize, or return to within Baseline values. ^d

Table 9-6: Required investigations and follow up for PDILI

Laboratory value		Symptoms ^a of hepatitis or hypersensitivity	Immediate		Follow up	
ALT or AST	Total bilirubin		Consultation requirements	Actions	Testing	Evaluation

ALP=alkaline phosphatase; ALT=alanine aminotransferase; ASAP=as soon as possible; AST=aspartate aminotransferase; HCP=healthcare practitioner; IMP=investigational medicinal product; NA=not applicable; PDILI=potential drug-induced liver injury; ULN=upper limit of normal

^a Hepatitis symptoms include fatigue, nausea, vomiting, and right upper quadrant pain or tenderness; hypersensitivity symptoms include eosinophilia (>5%), rash, and fever (without clear alternative cause).

^b If the study participant also has $\geq 2 \times$ ULN ALP, the possibility of an indication of biliary obstruction should be discussed with the Medical Monitor.

^c Details provided in Section 9.2.1.1. The local hepatologist is the expert usually consulted by the treating physician for assessment and management of potential hepatic disease. This would usually be a hepatologist, but may be a gastroenterologist.

^d Unless an alternative monitoring schedule is agreed by the investigator and UCB responsible physician. Determination of stabilization is at the discretion of the investigator in consultation with the hepatologist (as applicable) and UCB responsible physician, as needed.

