6.4.2 Potential drug-induced liver injury IMP discontinuation criteria

Study participants with potential drug-induced liver injury (PDILI) must be assessed to determine if IMP must be discontinued. In addition, all concomitant medications and herbal supplements that are not medically necessary should also be discontinued.

The PDILI criteria below require **immediate and permanent** discontinuation of IMP:

- Study participants with either of the following:
 - ALT or AST $\geq 5\text{xULN}$
 - ALT or AST $\geq 3\text{xULN}$ and coexisting total bilirubin $\geq 2\text{xULN}$

The PDILI criterion below requires immediate discontinuation of IMP:

- Study participants with ALT or AST $\geq 3\text{xULN}$ who exhibit temporally associated symptoms of hepatitis or hypersensitivity. Hepatitis symptoms include fatigue, nausea, vomiting, right upper quadrant pain or tenderness. Hypersensitivity symptoms include fever (without clear alternative cause), rash, or eosinophilia (ie, $>5\%$).

If a nondrug-related cause for the symptoms can be confirmed, these study participants may resume IMP administration after discussion with the responsible UCB physician, but only when the requirements for rechallenge with IMP as provided in Section 9.2.1.2.1 are followed.

The PDILI criterion below allows for study participants to continue on IMP at the discretion of the investigator.

- Study participants with ALT or AST $\geq 3 \times$ ULN (and $\geq 2 \times$ Baseline) and $< 5 \times$ ULN, total bilirubin $< 2 \times$ ULN, and no eosinophilia (ie, $\leq 5\%$), with no fever, rash, or symptoms of hepatitis (eg, fatigue, nausea, vomiting, right upper quadrant pain or tenderness).

Evaluation of PDILI must be initiated as described in Section 9.2.1. If study participants are unable to comply with the applicable monitoring schedule, IMP must be discontinued immediately.

Investigators should attempt to obtain information on study participants in the case of IMP discontinuation to complete the final evaluation. Study participants with PDILI should not be withdrawn from the study until investigation and monitoring are complete. All results of these evaluations and observations, as well as the reason(s) for IMP discontinuation and study participant withdrawal (if applicable), must be recorded in the source documents. The eCRF must document the primary reason for IMP discontinuation.

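### The liver stopping rules overlap for symptomatic participants with ALT/AST ≥5xULN and bilirubin <2xULN, and Table 9-6 leaves one asymptomatic ≥5xULN case without a row

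*Protocol*

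**What the plan says.** Protocol Section 6.4.2 sets three levels.

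- Permanent stop: "The PDILI criteria below require immediate and permanent discontinuation of IMP". Two criteria follow: ALT or AST ≥5xULN, or ALT or AST ≥3xULN with bilirubin ≥2xULN. Neither depends on symptoms or on a multiple of Baseline.
- Immediate stop, not labelled permanent: participants with ALT or AST ≥3xULN "who exhibit temporally associated symptoms of hepatitis or hypersensitivity". No upper limit is set on enzymes or bilirubin. If a nondrug cause of the symptoms is established, the section states that "these study participants may resume IMP administration after discussion with the responsible UCB physician". It makes this subject to the restart conditions of 9.2.1.2.1.
- Continuation at the investigator's discretion: ≥3xULN (and ≥2x Baseline) to <5xULN, bilirubin <2xULN, no symptoms.

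Table 9-6 has four rows:

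1. ≥3xULN, bilirubin ≥2xULN, any symptom status: permanent stop.
2. ≥3xULN, any bilirubin, symptoms present: "Immediate, temporary or permanent, IMP discontinuation".
3. ≥3xULN (and ≥2x Baseline) to <5xULN, bilirubin <2xULN, no symptoms: an immediate stop is not required.
4. "≥5xULN (and ≥2x Baseline"), bilirubin <2xULN, no symptoms: permanent stop.

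Section 9.2.1 says "The PDILI IMP discontinuation criteria for this study are provided in Section 6.4.2". For any stop made under that section it adds that "IMP must be permanently discontinued unless a subsequent alternative diagnosis fully explains the hepatic findings". Section 9.2.1.2 sends the reader to Table 9-6 and to Section 6.4.1 for the action, and 9.2.1.2.1 repeats the 6.4.1 reference. Section 6.4.1 deals with infection and low IgG and contains no liver criteria.

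**The concern.** A mandatory liver stopping rule should give one answer for each participant. For a symptomatic participant at ≥5xULN with bilirubin <2xULN, Section 6.4.2 gives both a permanent stop and a resumable one, and the table offers only the row that permits a temporary stop. An asymptomatic participant with the same values at ≥2x Baseline gets an expressly permanent row. The Baseline qualifier in row 4, which 6.4.2 does not carry, leaves another group with no row at all.

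The scope of rechallenge is also stated in three ways. Section 6.4.2 offers resumption only under the symptomatic criterion, 9.2.1 opens it after every 6.4.2 stop, and 9.2.1.2.1 refers to criteria that it does not name. At stake is whether a site treats a stop as final, and which stops it may put forward for rechallenge.

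**Working it through.** There is no planned figure to reproduce. The check takes each combination of ALT/AST, bilirubin, symptoms and (where a rule uses it) the multiple of Baseline, and lists every 6.4.2 criterion and every table row that it meets. Enzymes and bilirubin are in multiples of ULN; BL is Baseline.

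| ALT/AST | Bilirubin | Symptoms | Section 6.4.2 | Table 9-6 |
|---|---|---|---|---|
| 3 to <5 | <2 | No, ≥2x BL | may continue | row 3, may continue |
| 3 to <5 | <2 | No, <2x BL | no criterion | no row |
| 3 to <5 | <2 | Yes | stop, resumable | row 2 |
| 3 to <5 | ≥2 | No | permanent | row 1, permanent |
| 3 to <5 | ≥2 | Yes | permanent; also symptomatic criterion | row 1, permanent; also row 2 |
| ≥5 | <2 | No, ≥2x BL | permanent | row 4, permanent |
| ≥5 | <2 | No, <2x BL | permanent | **no row** |
| ≥5 | <2 | Yes | permanent; also symptomatic criterion | **row 2 only** |
| ≥5 | ≥2 | No | permanent | row 1, permanent |
| ≥5 | ≥2 | Yes | permanent; also symptomatic criterion | row 1, permanent; also row 2 |

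Results:

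- Where 6.4.2 has a permanent criterion, the table lacks an expressly permanent row in the two lines in bold.
- The symptomatic bold line does not depend on Baseline, because neither the 6.4.2 criterion at ≥5xULN nor row 2 uses it.
- The two symptomatic lines with bilirubin ≥2xULN also overlap, but a permanent row applies in each, so this matters little.
- In the second line both texts are silent. They do not conflict there.

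How narrow is the no-row case? At ALT/AST of x times ULN, being below 2x Baseline means Baseline above x/2 times ULN: above 5/2 = 2.5xULN at 5xULN, and above 8/2 = 4xULN at 8xULN. Exclusion criterion 7 bars entry above 2xULN. If Baseline is an entry value that met this limit, 2 × 2 = 4xULN is below 5xULN, so the gap cannot arise. Section 4 of the protocol takes Baseline for direct enrollees from the parent study, whose liver limits are not in these documents. The gap is open for them only if that Baseline exceeded 2.5xULN.

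**The case against.** The strongest defence is that the table does not break a clean rule. The overlap starts inside 6.4.2, where the symptomatic criterion is uncapped. Read literally, that criterion makes the symptomatic participant at ≥5xULN resumable, and row 2 then agrees with it. Row 2 also allows a permanent stop, so a site that stops permanently satisfies both texts. Section 9.2.1 names 6.4.2 as the source of the criteria and presents the table as a summary of the investigation. All of this stands, and it is why the fix must start in 6.4.2. It does not settle the matter, because no text says which criterion prevails, and 9.2.1.2 directs the site to the table and to a section without liver criteria.

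A reader might infer that symptomatic participants are managed less strictly overall. The documents do not support that. If the consultation and testing cells are shared by rows 1 and 2, as the extracted layout suggests, symptomatic participants need a hepatology consultation and testing as soon as possible. Row 4 requires hepatology only at ≥8xULN and sets 48 hours for testing.

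A reader might also infer that dosing could simply resume after row 2. It could not. Section 9.2.1.2.1 demands all 8 conditions, among them a confirmed nondrug cause, no alternative treatment, clear benefit, bilirubin <1.5xULN, no signs of hypersensitivity, and approval by the sponsor's physician, the DMC and a hepatologist.

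**Conclusion.** The concern holds as a minor safety-conduct correction. In two combinations of laboratory values and symptoms the table does not deliver the permanent stop that 6.4.2 requires at ≥5xULN: symptomatic with bilirubin <2xULN (row 2 only), and asymptomatic below 2x Baseline with bilirubin <2xULN (no row). The first follows from an overlap that 6.4.2 and the table share. The second comes from a qualifier found only in the table.

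The two combinations are not a measure of clinical weight: the documents give no event rate, and the sample size is redacted. IMP stops immediately on every reading of 6.4.2. What stays unclear is whether the stop is final and which stops are open to rechallenge.

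It would be tempting to carry the point into the results, but no planned analysis depends on it. SAP Section 10.3.1 tabulates liver findings by its own thresholds. The conclusion assumes that the extracted rows of Table 9-6 are faithful; the cells used here are legible and consistent with each other.

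**What to change.** - In both 6.4.2 and row 2 of Table 9-6, cap the symptomatic criterion at ALT/AST ≥3xULN to <5xULN with bilirubin <2xULN.
- Make the table's ≥5xULN row permanent regardless of symptoms, and delete its ≥2x Baseline qualifier so that it matches 6.4.2. Both edits are needed: with row 2 capped and the qualifier kept, a symptomatic participant at ≥5xULN but <2x Baseline with bilirubin <2xULN would match no row. Keep the stricter consultation and testing for symptomatic participants.
- Limit rechallenge in 9.2.1 and 9.2.1.2.1 to the capped symptomatic criterion, the only one for which 6.4.2 offers resumption.
- Change the references to Section 6.4.1 in 9.2.1.2 and 9.2.1.2.1 to 6.4.2.

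After these edits every combination at ≥5xULN, and every one with bilirubin ≥2xULN, leads to a permanent stop in both places, and row 2 covers only the resumable case. The cost is a protocol text and table edit, with no added tests, visits or analyses.
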